4.2 Scientific Rationale for Study Design

This study is a randomized, double-blind, -placebo controlled, parallel-group, dose-ranging study. The study population includes participants 18 to 70 years of age with moderate to severe chronic plaque psoriasis. The population selected for this study reflects a standard population for moderate to severe psoriasis trials with new treatment interventions like DC-806.

Placebo control will be used in this study to address potential confounding factors, such as potential Investigator bias in safety and efficacy assessments, or regression to the mean in endpoint scoring. In addition, due to the nature of psoriasis and the outcome measures used, a placebo arm is necessary to obtain reliable efficacy measurements. Moreover, the inclusion of a placebo group is in accordance with health authority guidelines (European Medicines Agency, Committee For Medicinal Products For Human Use 2004), provides an accurate determination of efficacy and safety findings attributable to DC-806, minimizes bias, and is a standard requirement to ascertain study sensitivity due to the seasonal and fluctuating character of chronic plaque psoriasis.

Standard statistical, clinical, and laboratory procedures will be utilized in this study. All efficacy measurements in this study are standard for assessing disease activity in patients with psoriasis.

4.3 Dose Selection Rationale

The rationales of selecting these different dose regimens are:

- To evaluate a wide exposure range to characterize the exposure-response relationship and define the therapeutic window for DC-806
 - C_{trough} concentrations will cover an exposure range of ~8-fold
- To identify exposure driver(s) for efficacy or safety (if any) and determine the appropriate "exposure target" for future studies
- Both QD and BID regimens will be evaluated to understand the contribution of "time above target" in achieving the desired clinical benefit
 - o Identify a feasible QD regimen that is efficacious and safe

4.4 End of Study Definition

End of Study is defined as the date when all participants have had a Follow-up Visit (Day 115), Early Termination Visit, or have otherwise been discontinued from the study. Primary completion is defined as the last date on which data for the primary endpoints are collected.

The Sponsor may decide to terminate the study at any time, if appropriate (Section 7.1).

5.0 STUDY POPULATION

The following eligibility criteria are designed to select participants for whom participation in the study is considered appropriate. All relevant medical and non-medical conditions should be taken into consideration when deciding whether a particular participant is suitable for this protocol. Participant eligibility should be reviewed and documented by an appropriate member of the Investigator's study team before participants are included in the study.

5.1 Inclusion Criteria

Participants are eligible to be included in this study only if all of the following criteria apply:

Age

1. Must be 18 to 70 years of age, inclusive, at the time of signing the ICF

Type of Participant and Disease Characteristics

- 2. Must have a BMI of 18 to 40 kg/m²
- 3. Must meet all of the following psoriasis criteria:
 - Clinical diagnosis of plaque psoriasis for ≥6 months before the Baseline visit
 - Stable moderate to severe chronic plaque psoriasis, defined as ≥10% BSA psoriasis involvement, sPGA score of ≥3, and PASI score ≥12 at the Screening and Baseline visits
 - Candidate for phototherapy or systemic therapy, as assessed by the Investigator

Sex and Reproductive Status

4. Male or female

Contraceptive use by female participants should be consistent with local regulations regarding the methods of contraception for those participating in clinical studies (Section 10.5).

- Female participants must be postmenopausal or permanently sterilized, or, if a WOCBP, must be willing to use a highly effective method of contraception during the study and for ≥30 days after last dose of study drug
- Female participants must not be pregnant, lactating, or planning pregnancy during the study and for ≥30 days after last dose of study drug

Informed Consent

- 5. Participants or their legally authorized representative must voluntarily sign and date an informed consent approved by an Independent Ethics Committee (IEC)/Institutional Review Board (IRB), before the initiation of any screening or study-specific procedures
- 6. Participants must be willing and able to comply with scheduled visits, treatment plan, laboratory tests, lifestyle considerations, and other study procedures
- 7. Participants must be willing to discontinue topical and/or systemic therapies for psoriasis before the first dose of study drug
- 8. Participants must agree to avoid prolonged exposure to the sun and to refrain from the use of tanning booths, sun lamps, and other sources of ultraviolet light during the study

5.2 Exclusion Criteria

Participants are excluded from the study if any of the following criteria apply:

Medical Conditions

- 1. Have had a clinically significant flare of psoriasis during the 12 weeks before the Baseline visit, as assessed by the Investigator
- 2. History of erythrodermic psoriasis, generalized or localized pustular psoriasis, predominantly guttate psoriasis, medication-induced or medication-exacerbated psoriasis
- 3. Have any known or suspected diagnosis of inflammatory conditions other than psoriasis and psoriatic arthritis, including but not limited to rheumatoid arthritis, sarcoidosis, IBD (Crohn's disease or ulcerative colitis), or systemic lupus erythematosus. Participants with a diagnosis of psoriatic arthritis requiring and/or are currently receiving systemic immunosuppressant medical treatment (including corticosteroids, immunosuppressants, biologics) are excluded from the study.
- 4. Have any active skin disease other than psoriasis that could interfere with the assessment of psoriasis
- 5. History of chronic infections including HIV or viral hepatitis (HBV, HCV):
 - Positive test for HIV

OR

Positive test for hepatitis B surface antigen (hBsAg): participants who are hBsAg
negative, hepatitis B core antibody (hBcAb) positive, and hepatitis B surface antibody
(hBsAb) positive at Screening will have reflex testing for HBV DNA by polymerase
chain reaction (PCR); participants who have HBV DNA above the lower limit of
quantification are excluded

OR

 Positive test for hepatitis C antibody and a positive confirmatory test for HCV RNA (detectable HCV by PCR)

6. History of active TB

- Participants with a positive IGRA or a purified protein derivative test result may participate in the study if further work up (according to local practice/guidelines) establishes conclusively that the participant has no evidence of active TB
- If a negative purified protein derivative test has been documented in the 3 months before Screening, it does not need to be repeated
- If presence of latent TB is established, participants are not required to be treated with prophylactic anti-TB therapy before or during the study, if the participant is considered low risk for reactivation per Investigator judgment
- 7. History or evidence of active infection (including but not limited to COVID-19 infection) and/or febrile illness within 7 days, serious infections leading to hospitalization and intravenous antibiotic treatment within 90 days, or serious infection requiring antibiotic treatment within 30 days before the first dose of study drug
- 8. History of malignancy or lymphoproliferative disease except resected cutaneous squamous cell or basal cell carcinoma that has been treated without recurrence
- 9. Participant has previously received a solid organ transplant
- 10. Presence of active suicidal ideation, or positive suicide behavior using the "Baseline /Screening" version of the C-SSRS and with either of the following criteria:
 - History of suicide attempt (including an actual attempt, interrupted attempt, or aborted attempt) within 5 years before the Screening visit; participants with a history of a suicide attempt >5 years ago should be evaluated by a mental healthcare professional (eg, locally licensed psychiatrist, psychologist, or master's level therapist) before enrolling into the study
 - Suicidal ideation in the past month before the Screening visit as indicated by a positive response ("Yes") to either Question 4 or Question 5 of the "Baseline/Screening" version of the C-SSRS at Screening
- 11. History or evidence of hepatic impairment (eg, history or presence of ascites, encephalopathy, prolonged prothrombin time, hypoalbuminemia, or hyperbilirubinemia); history of any current serious or unstable illnesses including renal, gastrointestinal, respiratory, cardiovascular (including ischemic heart disease), endocrinologic, neurologic, psychiatric, immunologic, or hematologic disease or other conditions that, in the Investigator's opinion, could interfere with the analyses of safety and efficacy in this study
- 12. Have undergone major surgery within 12 weeks before the first dose of study drug or planned to be performed during the study (eg, hip replacement, aneurysm removal, stomach ligation) as assessed by the Investigator
- 13. Have a history of alcohol or substance abuse within 6 months before the first dose of study drug that in the opinion of the Investigator will preclude participation in the study
- 14. History of an allergic reaction or hypersensitivity to constituents of the study drug (and its excipients) and/or other products in the same class

Prior/Concomitant Therapy

- 15. Participant has received a live or attenuated vaccine within the 6 weeks before the first dose of study drug
- 16. Participant has experienced primary failure (no response at approved doses after ≥3 months of therapy) to one or more therapeutic agents targeted to IL-17 (including but not limited to secukinumab, ixekizumab, brodalumab, bimekizumab)
- 17. Received anti-TNFα inhibitor(s) or agents that modulate B cells or T cells (eg, alemtuzumab, abatacept, alefacept) within 12 weeks or 5 half-lives (whichever is longer) before the first dose of study drug
- 18. Received any therapeutic agent directly targeted to IL-17 (including but not limited to secukinumab, ixekizumab, brodalumab, and bimekizumab) within 16 weeks or 5 half-lives (whichever is longer) before the first dose of study drug
- 19. Received ustekinumab, risankizumab, tildrakizumab, guselkumab, efalizumab, mirikizumab, or other IL-23 inhibitors within 24 weeks or 5 half-lives (whichever is longer) before the first dose of study drug
- 20. Received rituximab within 1 year before the first dose of study drug (or within 6 months if B cells have returned to pretreatment level or normal reference range [local laboratory] if pretreatment levels are not available)
- 21. Received any systemic nonbiologic therapy for psoriasis, including but not limited to methotrexate, cyclosporine, corticosteroids, oral retinoids, deucravacitinib, apremilast, and fumaric acid derivatives within 4 weeks before the first dose of study drug
- 22. Received phototherapy, laser therapy, tanning booth, or extended sun exposure that could affect psoriasis disease severity or interfere with disease assessments within 4 weeks before the first dose of study drug
- 23. Received topical medications including but not limited to, corticosteroids, anthralin, calcipotriene, topical vitamin D derivatives, retinoids, urea, alpha- or beta-hydroxyl acids, and medicated shampoos (eg, those that contain >3% salicylic acid, corticosteroids, coal tar or vitamin D3 analogues) within 2 weeks before the first dose of study drug; participants are allowed to use bland (containing no psoriasis treatment) emollients and bland shampoos during the study
- 24. Received an experimental antibody or biologic therapy within the previous 6 months or 5 half-lives (whichever is longer), or received any other experimental therapy or new investigational agent within 30 days or 5 half-lives (whichever is longer) before the first dose of study drug, or is currently enrolled in an investigational study
- 25. Systemic use of known strong and moderate CYP3A4 inhibitors or strong CYP3A4 inducers from Screening through the end of the study (refer to Section 0)

Diagnostic Assessments

- 26. A 12-lead ECG at Screening that demonstrates clinically significant abnormalities or criteria associated with QT interval abnormalities, including prolongation of QTcF interval (>500 msec)
- 27. Laboratory values meeting the following criteria within the Screening period before the first dose of study drug:
 - Serum AST ≥2×ULN
 - Serum ALT ≥2×ULN
 - Serum total, direct, or indirect bilirubin ≥2.0 mg/dL; except for participants with isolated elevation of indirect bilirubin relating to a confirmed diagnosis of Gilbert syndrome
 - Serum albumin ≤3.5 g/dL
 - Prothrombin time ≥4 seconds or International Normalized Ratio ≥1.7
 - Estimated GFR by simplified 4-variable MDRD formula <45 mL/min/1.73m²
 - Total white blood cell count <3000/μL
 - Absolute neutrophil count <1500/μL
 - Platelet count <100,000/μL
 - Hemoglobin <9 g/dL
- 28. In the opinion of the Investigator or Sponsor, have any uncontrolled clinically significant laboratory abnormality that would affect interpretation of study data or the participant's enrollment in the study

Other Exclusion Criteria

- 29. Participants who are incapacitated, prisoners or involuntarily incarcerated, in compulsory detention for treatment of either a psychiatric or physical illness, or in other situations that render the participant vulnerable according to local regulations
- 30. Participants who are employees of the Sponsor or third-party organizations involved in this study or are Investigator-site personnel directly affiliated with this study and/or their immediate families (defined as a spouse, parent, child, or sibling, whether biological or legally adopted)

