8.0 STUDY ASSESSMENTS AND PROCEDURES

Every effort should be made to ensure that protocol required assessments and procedures are completed as described. However, it is anticipated that from time to time there may be circumstances outside the control of the Investigator that may make it unfeasible to perform an assessment. In these cases, the Investigator must take all steps necessary to ensure the safety and wellbeing of the participant.

Guidance on the conduct of study procedures in the context of COVID-19 or other virus/infection or public health related travel restrictions or emergency is described in Section 10.6. When a protocol required assessment cannot be performed, the Investigator will document the reason for the missed assessment and any corrective and preventive actions that he or she has taken to ensure that required processes are adhered to as soon as possible. The study team must be informed of these incidents in a timely manner.

Guidance on study procedures, their timing, and expected order of completion are summarized in the Schedule of Assessments (Section 1.3), Section 8.0, and the Study Reference Manual. Protocol waivers or exemptions are not allowed.

Immediate safety concerns should be discussed with the Sponsor immediately upon occurrence or awareness to determine if the participant should continue or discontinue study intervention.

Adherence to the study design requirements, including those specified in the Schedule of Assessments (Section 1.3), is essential and required for study conduct.

All screening evaluations must be completed and reviewed to confirm that potential participants meet all eligibility criteria. The Investigator will maintain a screening log to record details of all participants screened and to confirm eligibility or record reasons for screening failure, as applicable. The Investigator (or delegate) will obtain informed consent from each participant, in accordance with the procedures described in Section 10.1.3.

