#### 9.2. Clinical Laboratory Evaluations

All summaries will be based on SI units. Blood and urine samples collected at the times indicated in the schedule of events (see Appendix 15.1) for clinical laboratory values (hematology, clinical chemistry, coagulation, urinalysis, and virology) will be analyzed by the central laboratory. COVID-19 testing will be performed on site or by the site's local laboratory. Clinical follicle stimulating hormone tests will be performed by the central laboratory. Additional blood, urine, and/or throat swab samples may be taken for safety tests.

Summary tables presenting observed values and changes from baseline will be presented for clinical laboratory tests with numeric values by treatment group for participants in the SAS. One table will be presented for each of hematology, and clinical chemistry parameter categories. Summary of observed values at screening for coagulation will be presented.

A table for categorical urinalysis values over time and screening virology will also be presented.

The number and proportion of participants with normal, high, and low values for each laboratory test (hematology and clinical chemistry) will be presented by visit and treatment group according to the reference ranges in the Central Lab Manual.

The number and proportion of participants with CTCAE Grades for each laboratory test (hematology and clinical chemistry) will be presented by visit and treatment group.

Shift tables summarizing the baseline and post-baseline timepoints results using normal range and CTCAE grading when available for clinical laboratory tests (hematology and clinical chemistry) will be displayed in cross-tabulations. Only during treatment endpoints are considered in this summary. Unscheduled assessments are included in the table for calculation of minimum post-baseline and maximum post-baseline values.

Corresponding box plots by visit and treatment of the observed values will also be presented for hematology parameters:

- Hemoglobin
- White blood cell count

- Neutrophils
- Lymphocytes
- Platelet count
- Erythrocyte sedimentation rate

and clinical chemistry parameters:

- Albumin
- Alkaline phosphatase
- Alanine aminotransferase
- Aspartate aminotransferase
- Total Bilirubin
- creatinine
- C-reactive protein
- Estimated glomerular filtration rate
- Gamma glutamyl transferase
- Lactate dehydrogenase
- Total cholesterol
- High-density lipoprotein cholesterol
- Low-density lipoprotein cholesterol

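### Exclusion 27 sets the prothrombin time limit at an absolute 4 seconds with no reference value, so as written it excludes essentially everyone and makes the INR limit redundant

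*Protocol*

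**What the plan says.** Criterion 27 opens with "Laboratory values meeting the following criteria within the Screening period before the first dose of study drug" and includes the bullet "Prothrombin time ≥4 seconds or International Normalized Ratio ≥1.7". The Key Exclusion Criteria in the synopsis (Section 1.1) carry the same bullet in the same words.

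Three other provisions determine how it operates:

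- The exclusion list in Section 5.2 begins "Participants are excluded from the study if any of the following criteria apply", so one met criterion is enough.
- Section 8.0 states "Protocol waivers or exemptions are not allowed".
- SAP Section 9.2 states "Summary of observed values at screening for coagulation will be presented", so PT values are expected to exist at screening.

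Neither document says what the 4 seconds are measured against. Appendix 2 of the protocol (Section 10.2) lists prothrombin time and INR without ranges. The SAP sets no PT limit. Criterion 11 names, as examples of hepatic impairment, "history or presence of ascites, encephalopathy, prolonged prothrombin time, hypoalbuminemia, or hyperbilirubinemia", which has the idea of prolongation but no number. Within criterion 27 the transaminase limits do carry a reference ("Serum AST ≥2×ULN"), while others, such as albumin and hemoglobin, are absolute values.

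**The concern.** PT is reported in seconds, and INR is that time divided by the laboratory's mean normal time, raised to a power. A limit in seconds therefore means something only if it is an absolute time of sensible size or an excess over a stated reference. Here it is written as an absolute time, and 4 s looks far too short to separate normal from abnormal clotting.

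If so, the PT half is met by people whose INR is normal. Because the two halves are joined by an or, the INR half then adds nobody. With one criterion sufficient and waivers barred, a site that follows the text has no permitted route to enrol a person with ordinary clotting. A site that departs from the text has to supply its own reference for a criterion that screens liver synthetic function.

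**Working it through.** The plan states no calculation to reproduce. The check is whether the two halves of the bullet can describe a comparable limit.

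**Inputs from the documents.** PT limit 4 s, absolute; INR limit 1.7; joined by or.

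**Assumed inputs (not in the documents).** Mean normal PT M from 9 to 15 s and ISI from 1.0 to 2.0. For the population share, PT is taken as normally distributed with mean 10 to 14 s and SD 0.5 to 2 s.

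**Step 1: the INR that an absolute 4 s represents.** INR = (PT / M)^ISI.
- ISI 1, M = 9: 4/9 = 0.44.
- ISI 1, M = 15: 4/15 = 0.27.
- A higher ISI pushes this lower still: at ISI 2 the values are 0.44² = 0.20 and 0.27² = 0.07.

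**Step 2: the PT that INR 1.7 represents.** At ISI 1, PT = 1.7 × M.
- M = 9: 15.3 s.
- M = 15: 25.5 s.

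The two limits in the one bullet thus sit at about 4 s and at 15.3 to 25.5 s.

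**Step 3: when would they coincide?** Solve (4 / M)^ISI = 1.7, so M = 4 / 1.7^(1/ISI).
- ISI 1.0: 4 / 1.7 = 2.35 s.
- ISI 1.5: 2.81 s.
- ISI 2.0: 4 / 1.304 = 3.07 s.

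The INR half could catch someone whom the PT half misses only if the mean normal PT were below these values, well under the assumed range.

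**Step 4: share of people meeting the PT half.** P(PT ≥ 4) = 1 − Φ((4 − mean) / SD).

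| Mean PT (s) | SD 0.5 | SD 1 | SD 1.5 | SD 2 |
|---|---|---|---|---|
| 10 | 1.00000 | 1.00000 | 0.99997 | 0.99865 |
| 12 | 1.00000 | 1.00000 | 1.00000 | 0.99997 |
| 14 | 1.00000 | 1.00000 | 1.00000 | 1.00000 |

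The lowest cell is Φ(3) = 0.99865, or about 99.87%.

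**Step 5: does reading it as a prolongation settle the matter?** For comparison only, a PT of 4 s above the mean normal gives INR = ((M + 4) / M)^ISI. That runs from 19/15 = 1.27 (M = 15, ISI 1) to (13/9)² = 2.09 (M = 9, ISI 2). This is the same order as 1.7, but the figure depends on the reference and reagent, and a reference at the upper limit of normal would give different values again. The reading is plausible, but it still needs a stated reference.

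**The case against.** The strongest reply is that any site will see a dropped qualifier. Criterion 11 speaks of a prolonged PT, the INR limit on the same line works, and no one would screen out the whole population on a slip. That is probably right about behaviour, and it limits the consequences in four ways.

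- **The halves do not contradict each other.** Two exclusions joined by an or can both stand when one covers the other; the narrower one is simply redundant.
- **A reader might infer that every enrolled participant becomes a recorded eligibility violation.** The documents do not support this. SAP Section 6.4 lists criteria not met, but nothing says the listing is derived from the PT values. A site that reads the limit as prolongation would record the criterion as satisfied. SAP Section 5.2 has deviations classified in cooperation with the sponsor.
- **A reader might infer that people with impaired liver synthetic function get in.** The literal error runs towards excluding too many. Criterion 11, the INR, albumin, bilirubin and transaminase limits in criterion 27, and the judgement clause in criterion 28 all still operate.
- **Variation between sites is bounded.** Protocol Section 8.2.5.1 and SAP Section 9.2 place coagulation testing at the central laboratory. The reference ranges that the SAP cites from the Central Lab Manual are for hematology and chemistry.

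It is also fair that the size of the effect rests on outside figures for a normal PT. What survives is that the reply concedes that the rule in use would not be the rule as written. One laboratory narrows the room for interpretation, but it does not say whether the seconds count from a control, a mean or an upper limit.

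**Conclusion.** The PT half of criterion 27 is wrong as written, in the main text and in the synopsis. Under the assumed mean normal PT of 9 to 15 s (ISI 1) it equates to an INR of about 0.27 to 0.44. Under the assumed distributions it is met by about 99.87% of people or more. The conclusion does not turn on a particular value: it holds for any mean normal PT well above 4 s.

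It would be tempting to conclude that the trial cannot enrol anyone. That follows only from literal application, which sites would probably not follow. The realistic effect is an eligibility rule that cannot be applied as written, with possible inconsistent application across the 60 to 65 planned sites and eligibility deviations that clearer wording would avoid. Eligibility is settled before randomization, so this does not bias the comparison between arms, and the sample size and primary test are untouched. It should be corrected, but it does not threaten the trial's conclusions.

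**What to change.** In Protocol Section 5.2, criterion 27, and in the synopsis, state what the PT seconds are measured against, and reconcile the PT half of the bullet with the INR half so that both can operate. The reference and the threshold are for the sponsor's clinical team to set; this review proposes neither.

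Check the regional versions as well. Section 12.0 shows a separate Amendment 2.0 for Czechia, Germany, Hungary, Poland and Spain. Its text is not among the documents reviewed, and any version with the same wording needs the same correction.

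The cost is a few words in each place at the next amendment, with no change to procedures, sample size or analysis.

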8.2.5.1 Hematology, Clinical Chemistry, Coagulation, Urinalysis and Virology

Site standard collection and processing procedures for blood and urine samples will be adhered to throughout the study. Scheduled blood samples for fasting lipid panel and fasting glucose will be taken following a ≥ 8 hour fast (water is permitted). Laboratory tests will be performed by the central laboratory.

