**In addition to repeating measurements of ALT, AST, ALP, and total bilirubin for suspected cases of potential drug-induced liver injury, additional laboratory tests should include, but are not limited to; albumin, creatine kinase, direct and indirect bilirubin, gamma-glutamyl transferase, and prothrombin time/international normalized ratio. Consideration should also be given to drawing a separate tube of clotted blood and an anticoagulated tube of blood for further testing, as needed, for further contemporaneous analyses at the time of the recognized initial abnormalities to determine alternative etiology.

⁺A detailed history including relevant information (eg, review of ethanol, acetaminophen/paracetamol [either by itself or as a coformulated product in prescription or over-the-counter medications], recreational drug use, supplement [herbal] use and consumption, family history, sexual history, travel history, history of contact with a jaundiced person, surgery, blood transfusion, history of liver or allergic disease, and potential occupational exposure to chemicals) should be collected. Further testing may be warranted (such as testing for acute viral hepatitis (A, B, C, D, and E) infection, liver imaging (eg, biliary tract), or serum drug levels (eg, acetaminophen/paracetamol). The Investigator should contact the Sponsor to discuss the management of a participant when an alternative etiology has been determined. The alternative etiology should be documented appropriately in the eCRF. Study drug should be discontinued if no alternative etiology can be found.

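### The prothrombin-time exclusion is written as an absolute 4 seconds with no comparator; the threshold is wrong as written, and a minor wording correction in two places fixes it

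*Protocol*

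**What the plan says.** Protocol Section 5.2, criterion 27, lists laboratory values that exclude a candidate during screening. The coagulation line is "Prothrombin time ≥4 seconds or International Normalized Ratio ≥1.7", and the key exclusion criteria in the synopsis use the same words.

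In the same list the transaminase limits carry a comparator, for example "Serum AST ≥2×ULN". The limits for bilirubin, albumin, blood counts and hemoglobin are absolute values with units, and those work as absolute values.

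The section opens with "Participants are excluded from the study if any of the following criteria apply", so meeting one line is enough. Section 8.0 adds that "Protocol waivers or exemptions are not allowed".

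Two neighbouring criteria overlap with the line. Criterion 11 gives "prolonged prothrombin time, hypoalbuminemia, or hyperbilirubinemia" among its examples of hepatic impairment. Criterion 28 lets the Investigator or Sponsor exclude candidates who "have any uncontrolled clinically significant laboratory abnormality that would affect interpretation of study data".

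**The concern.** A limit given in seconds has the form of an absolute value, like the albumin or platelet limits beside it. In that form it cannot be used, because a normal result meets it. The line makes sense only as a prolongation over some reference, and the reference is missing.

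What is at stake is a clear entry threshold for hepatic safety. A site following the text exactly would exclude its candidates. A site that infers a prolongation must choose the reference itself, and two sites could choose differently. The plan foresees 60 to 65 sites (Protocol synopsis). Screen failures need not be entered in the eCRF (Protocol Section 5.4), so inconsistent exclusions might not be seen.

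**Working it through.** **1. Is a comparator given anywhere?** The documents mention prothrombin time or coagulation in these places:

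- Synopsis and Section 5.2, criterion 27: 4 seconds, no reference.
- Section 5.2, criterion 11: prolonged prothrombin time as an example, with no number and no reference.
- Section 10.2 (laboratory tests): the test is listed only.
- Section 10.4.1 (hepatotoxicity): "and prothrombin time/international normalized ratio" closes a list of additional tests, with no limit.
- SAP Section 9.2: screening coagulation values are summarized, with no limit.

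No comparator is stated. The wording is identical and unbroken in both places, so text lost in PDF reading is an unlikely explanation.

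**2. Literal reading.** The documents give no normal range. Assume a normal prothrombin time of 10 to 14 s. Then 4/14 = 0.286 and 4/10 = 0.400, so the limit is 29% to 40% of a normal value. Every normal result exceeds it, and so does every prolonged one.

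**3. Do the two halves of the line agree?** Use INR = (PT / mean normal PT)^ISI. Assume a mean normal PT of 10 to 14 s and an ISI of 0.9 to 1.3; neither is in the documents.

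- INR at PT = 4 s: from (4/14)^1.3 = 0.20 to (4/10)^0.9 = 0.44. The paired limit is 1.7.
- PT at INR = 1.7: from 10 × 1.7^(1/1.3) = 15.0 s to 14 × 1.7^(1/0.9) = 25.2 s. Anyone who meets the INR half has already met an absolute 4 s, so the INR half is redundant.
- Mean normal PT at which 4 s would equal INR 1.7: from 4/1.7^(1/0.9) = 2.2 s to 4/1.7^(1/1.3) = 2.7 s, far from the assumed 10 to 14 s.

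The halves cannot be reconciled if 4 s is absolute. A prolongation must have been meant.

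**4. Prolongation reading.** Assume further that the ULN lies 1.5 to 2.5 s above mean normal.

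| Reading | Threshold over the assumed range | Example: control 12 s, ULN 14 s |
|---|---|---|
| 4 s above control | 10 + 4 = 14 s to 14 + 4 = 18 s | 16 s |
| 4 s above ULN | 10 + 1.5 + 4 = 15.5 s to 14 + 2.5 + 4 = 20.5 s | 18 s |

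For a given laboratory the two thresholds differ by ULN minus control: 1.5 to 2.5 s on the assumptions, 2 s in the example. A candidate at 16 s to just under 18 s in the example is excluded on one reading and not on the other. At ISI 1 those values are INR 16/12 = 1.33 to 18/12 = 1.50, so the INR half does not decide the case there. These figures illustrate the size of the ambiguity; they are not estimates for this trial.

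**5. Does central testing settle it?** Section 8.2.5.1 says "Laboratory tests will be performed by the central laboratory". That supplies one control value and one ULN, but does not say which applies.

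**The case against.** The strongest reply is that nobody will apply the limit literally. Criterion 11 already speaks of prolongation, and any clinician would read 4 seconds that way. In the example, everyone in the disputed band is above the ULN of 14 s. If the prolongation is evidence of hepatic impairment, criterion 11 applies. If it is an uncontrolled, clinically significant abnormality that would affect the data or enrollment, criterion 28 applies. Those left over are few. The bar on waivers adds little, since clarifying an incomplete limit is not a waiver. The Study Reference Manual, Laboratory Manual and Central Lab Manual are not in hand and may hold a working definition.

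Most of this stands, and it limits the consequence. It does not make the line correct: a manual would not repair the protocol's wording, and inferring a prolongation does not name the reference.

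A reader might go further and infer any of the following, which the documents do not support:

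- **That the trial cannot enroll, or that hepatically impaired candidates would be admitted.** The first assumes a literal use that sites are very unlikely to make. The second overlooks criterion 11, criterion 28 and the other liver-related limits in criterion 27.
- **That control, or ULN, was plainly intended.** ULN is the only comparator in the list, but it is attached to other tests. Nothing points to control.
- **That the analysis is affected.** Membership of the full analysis set and the safety set depends on randomization and dosing (SAP Sections 4.4.3 and 4.4.4), not on this line.

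**Conclusion.** The threshold is wrong as written, in both places. That no comparator is given follows from the documents alone. That an absolute 4 s is unusable rests on the assumed normal range of 10 to 14 s, and holds throughout it.

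The practical effect is small. What remains unclear is a band about 1.5 to 2.5 s wide on assumed values, less the candidates whom criteria 11 and 28 already exclude. The number of candidates in it cannot be derived from the documents and is probably small. There is no effect on power, type I error or the analysis sets. This is a minor wording correction to a wrong eligibility threshold.

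**What to change.** In Section 5.2, criterion 27, and in the synopsis, insert one phrase directly after the 4 seconds and leave the INR half unchanged. The phrase is either *above ULN, as defined by the central laboratory* or *above control, as defined by the central laboratory*. The sponsor should confirm which was meant, and the same phrase should go in both places. Neither should be adopted by default.

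Section 12.0 of the Protocol lists a separate amendment for five European countries. That text is not available here, so the sponsor should check whether it carries the same line.

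The cost is one confirmation and one phrase in two places. No new test is needed and the SAP does not change.
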